### **9.1.3.2. Analysis of Clinical Labs**

Hematology and blood chemistry data will be graded according to NCI CTCAE version 4.0 severity grade if applicable. The frequencies of the worst severity grade observed will be displayed for each parameter. Summary tables of laboratory results by maximum CTC grade and shift tables of laboratory results from baseline by maximum CTC grade will be presented. Baseline is defined as the last evaluation prior to the first dose of study drug. For those hematology and blood chemistry tests that do not have CTC grades, summary tables of the laboratory results using flags (high/low) will be presented.

Listing tables will be prepared for each laboratory measure, and will be structured to permit review of the data by patient as they progress on treatment.

---

## Protocol A6181196 Statistical Analysis Plan - Version 1.0 Final

---

### **9.1.3.3. Concomitant Medications**

All medications received during the treatment period will be considered as concomitant medications and will be coded by WHO medical dictionary; patients who received concomitant medications will be listed.

### **9.1.3.4. Vital Signs**

Vital signs data will be summarized and presented by treatment group. Data will be summarized and presented according to the following categories:

Pulse Rate	>120 bpm or <50 bpm Change from baseline (increase or decrease) of $\geq 30$ bpm
Blood Pressure	Systolic BP >150 mmHg / Diastolic BP >100, or Systolic BP >200 mmHg / Diastolic BP >110 Change from baseline (increase) in SBP of $\geq 20$ , $\geq 40$ , or $\geq 60$ mmHg Change from baseline in DBP (increase) of $\geq 10$ , $\geq 20$ , or $\geq 30$ mmHg
Respiration Rate	>40/min or <8/min
Temperature	>38.3 °C (101 °F) Increase from baseline of $\geq 1.1$ °C ( $\geq 2$ °F) – if the baseline temperature is $>36.8$ °C (98.2 °F)
Body Weight	Percent change from baseline (increase or decrease) of $\geq 5\%$

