### **3. STUDY DESIGN**

This study is a single arm, multi-center, multi-national, clinical trial evaluating the PK, safety and preliminary anti-tumor efficacy of sunitinib in children and young adults diagnosed with advanced, unresectable GIST. The study aims to enroll 6 evaluable patients aged 6 years to less than 18 years. In addition, up to 15 young adults aged 18 - <21 years diagnosed with GIST may be enrolled.

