#### **4.1. Inclusion Criteria**

Patient eligibility should be reviewed and documented by an appropriately qualified member of the investigator's study team and confirmed with Pfizer before patients are included in the study.

Patients must meet all of the following inclusion criteria to be eligible for to commence study drug treatment into the study:

1. Histological diagnosis of GIST (refer to [Section 6.1](#));
2. Tumor tissue must be available to assess *KIT*, *PDGFRA*, and *BRAF* genotypes (for any of these genes where genotyping was not previously performed) and to assess succinate dehydrogenase (SDH) protein expression by immunohistochemistry. For exceptions see [Section 6.1](#);
3. Patients must have demonstrated disease progression or intolerance to imatinib mesylate; have GIST with non-mutant *KIT* (tumor genotyping may be performed prior to or during screening; patients with an indeterminate *KIT* genotype are eligible if genotyping performed during screening); or cannot obtain imatinib in their country.
4. Age 6 to <21 years;
5. Advanced, unresectable GIST for which there are no available options for treatment with curative intent as assessed by the investigator;
6. Measurable (per Response Evaluation Criteria in Solid Tumors; RECIST version 1.1; or evaluable disease (Refer to [Appendix 4](#));
7. Resolution of all acute toxic effects of prior cancer treatment, radiotherapy or surgical procedure to NCI CTCAE v4.0 grade  $\leq 1$ ;
8. ECOG Performance Status 0 -2 (for patients  $\geq 11$  years of age) or Lansky  $\geq 50\%$  (for patients  $< 11$  years);
9. Adequate organ function determined within 14 days prior to enrollment, defined by:
  - Peripheral absolute neutrophil count (ANC)  $\geq 1500/\mu\text{L}$ ;
  - Platelet count  $\geq 100,000/\mu\text{L}$ ;
  - Hemoglobin  $\geq 10 \text{ g/dL}$ ;
  - Total bilirubin  $\leq 1.5 \times$  upper limit of normal (ULN) for age;
  - ALT (SGPT) or AST (SGOT)  $\leq 3 \times$  ULN for age;
  - Serum albumin  $\geq 2.0 \text{ g/dL}$ ;

- Serum amylase and lipase <1.5 x ULN;
- Serum creatinine based on age/gender as follows:

Age	Maximum Serum Creatinine (mg/dL)	
	Male	Female
6 to <10 years	1	1
10 to <13 years	1.2	1.2
13 to <16 years	1.5	1.4
≥16 years	1.7	1.4

The threshold creatinine values in this table were derived from the Schwartz formula for estimating GFR (Schwartz et al. J. Peds, 106:522, 1985) utilizing child length and stature data published by the CDC.

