### **5.2.3. Sunitinib Administration**

A cycle of therapy is considered to be 42 days, with the reporting period for each cycle being Day 1 to Day 42. For all patients, sunitinib will be dosed intermittently [4 weeks on study drug followed by 2 weeks off therapy (Schedule 4/2)].

Sunitinib can be taken without regard to meals, but the incidence of drug-associated nausea may be less when taken with food. Therefore, it is recommended that sunitinib be taken with at least a small amount of food.

Self-administration of sunitinib capsules will take place on an outpatient basis (under parent/legal guardian supervision as appropriate) except on days when PK sampling is performed. Capsules should be taken once daily in the morning on the first 28 days of each cycle with the exception of study visit days on which the dose for that day should be withheld until immediately after the completion of all study visit day activities and the investigator's approval for continued dosing. Capsules must be administered whole, not opened, or manipulated prior to administration.

In the absence of progressive disease, patients may receive up to 18 cycles of sunitinib therapy for up to 24 months.

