### 7.2.4. Other Safety Assessments

- Height and body weight will be recorded prior to starting each treatment cycle for pediatric patients.

- Physical examination: A physical examination including, but not limited to, general, lungs, heart, abdomen, and extremities will be performed. The physical examination will include examination of known and suspected sites of disease.
- Performance Status: ECOG performance status scale will be used for patients  $\geq 11$  years of age or Lansky score for patients  $< 11$  years of age. Patients below the age of 11 who turn 11 while on-study will then require ECOG performance evaluations. (Refer to [Appendix 5](#));
- Vital signs: Measurements of temperature, blood pressure, heart rate and respiratory rate after 5 minutes of rest;
  - ECG: Three consecutive 12 lead ECGs (with a 10-second rhythm strip) will be collected approximately 2 minutes apart at screening, on Cycle 2 Day 1 (pre-dose) and at the end of treatment visit to determine the mean QTc interval. It is preferable that the machine used has a capacity to calculate the standard intervals automatically. If the mean QTc interval is prolonged ( $> 500$  msec), the ECGs should be overread by a cardiologist at the site for confirmation. Additional ECGs should be performed as clinically indicated, ie, after a new steady state of sunitinib is reached (ie, approximately 2 weeks) following:
    - Intrapatient sunitinib dose escalation, or
    - Intrapatient sunitinib dose reduction in response to:
      - a. QTc interval prolongation,
      - b. Significant electrolyte changes, vomiting, diarrhea, or addition of a strong CYP3A4 inhibitor listed in [Section 5.5.2](#) after consultation with the sponsor's medical monitor.

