### Appendix 3. Blood Pressure Levels for Girls and Boys by Age

The following tables were taken from “The Fourth Report on the Diagnosis, Evaluation, and Treatment of High Blood Pressure in Children and Adolescents” PEDIATRICS Vol. 114 No. 2 August 2004, pp. 555-576.

Instructions for using these BP Charts:

1. Measure the patient’s BP using an appropriate size cuff.
2. Select appropriate chart for a female or male patient.
3. Using the “age” row and “height” column, determine if the BP is within the ULN. The BP tables use height percentile data found on the CDC growth charts ([www.cdc.gov/growthcharts](http://www.cdc.gov/growthcharts)). See below.
4. See [Section 5.2.11](#) for suggested guidelines for medical treatment of sunitinib-related hypertension.

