#### 2.1. Study Design

This study is a single arm, multi-center, multi-national, Phase I/II trial evaluating the PK, safety and preliminary anti-tumor efficacy of sunitinib in chemotherapy-naïve children and young adults diagnosed with metastatic, unresectable (without major morbidity) or recurrent GIST. The study aims to enroll 15 evaluable children aged 6 years to less than 18 years. In addition, up to 15 young adults aged 18 years to less than 21 years may be enrolled. The starting dose of sunitinib in children will be 15 mg/m^2/day for 4 weeks followed by 2 weeks with no study drug, the MTD established during the pediatric Phase 1 clinical trial conducted by the Children's Oncology Group. Intrapatient dose escalation of sunitinib will be allowed, based on tolerability. Investigators will have the option to access real time PK results to aid in dosing decisions. Sunitinib dosing for the young adults will follow approved guidelines (per current USPI and SmPC). Study treatment for all patients may continue for up to 18 cycles, equaling approximately 2 years of therapy.

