## **9. STATISTICAL METHODOLOGY AND STATISTICAL ANALYSES**

Statistical analysis and data presentation will be performed on the subgroups of patients aged 6 years to less than 18 years, and patients aged 18 years to less than 21 years, respectively. A pooled data analysis including all the patients enrolled in the study will also be performed. Also, analysis of time-to-event efficacy endpoints will be performed only if sufficient number of events permit meaningful estimates.

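### The SAP's fixed 5% body-weight category has no growth reference, so in children still growing it can count expected gain and does not register weight that stays flat.

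*SAP*

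**What the plan says.** The body-weight row in SAP 9.1.3.4 (Vital Signs) is a single category: "Percent change from baseline (increase or decrease) of" 5% or more. It is not split by age or sex and is not tied to any growth standard.

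Eligibility in Protocol 4.1 is "Age 6 to <21 years". SAP Section 9 states that "Statistical analysis and data presentation will be performed on the subgroups of patients aged 6 years to less than 18 years", as well as in those aged 18 to under 21 and pooled, but it sets no separate criteria for children. The same row therefore applies to a 6-year-old and a 20-year-old.

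On duration, SAP 2.1 says "Study treatment for all patients may continue for up to 18 cycles, equaling approximately 2 years of therapy", and Protocol 5.2.3 says "A cycle of therapy is considered to be 42 days".

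On data, Protocol 7.2.4 says "Height and body weight will be recorded prior to starting each treatment cycle for pediatric patients". The SAP lists height only as a baseline characteristic (9.1.4). It plans no percentile, z-score or velocity for weight or height, and no analysis of the bone age and Tanner staging required by Protocol 7.3. SAP Section 2 ties the plan to the protocol dated 17 June 2011. The growth and pubertal assessments came in with Amendment 1, dated 11 June 2012.

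**The concern.** Percent change from a fixed baseline reads plainly when the expected change is zero, as in a fully grown patient. In a growing child the expected change is positive and increases with time on treatment. The row then mixes ordinary growth with anything the drug may do. It also stays silent in the case where a growing child stops gaining: no change from baseline is counted as no finding. A child who gains 5% and then stalls is counted only as an increase, which points the wrong way.

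At stake is how readable one descriptive safety display is for the paediatric group. That group is small: "The study aims to enroll 6 evaluable patients aged 6 years to less than 18 years". Each child counted moves the paediatric percentage by 100/6 = 16.7 points, so one or two children entering through growth alone would dominate the row.

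**Working it through.** **Inputs from the documents.** Cut-off 5% in either direction (SAP 9.1.3.4); up to 18 cycles (SAP 2.1); 42 days per cycle (Protocol 5.2.3); 6 children (Protocol Section 3).

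**Input assumed.** Annual proportional weight gain g in a growing child, taken as constant. The documents give no value. The working range is 5-12% per year, with 1-15% shown for sensitivity.

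**Step 1: the plan's own duration.** 18 × 42 = 756 days; 756/365.25 = 2.07 years, or 24.8 months. This agrees with the stated figure of approximately 2 years.

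**Step 2: the gain that reaches +5% by the end of treatment.** Formula: 1.05^(1/T) − 1.
- T = 2 years: 2.47% per year.
- T = 2.07 years: 2.39% per year.

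In kilograms, 5% is 1.0 kg from a 20 kg baseline and 2.0 kg from 40 kg. Over 2 years that is 0.5 and 1.0 kg per year.

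**Step 3: time to +5%, and the deficit of a child with flat weight.** Time in years = ln(1.05)/ln(1+g). Deficit against expected weight at 2 years = 1 − 1/(1+g)².

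| g per year | Months to +5% | Cycles to +5% | Flat-weight child at 2 years, below expected |
|---|---|---|---|
| 1% | not reached in 24.8 | – | 2.0% |
| 2% | not reached in 24.8 | – | 3.9% |
| 3% | 19.8 | 14.4 | 5.7% |
| 5% | 12.0 | 8.7 | 9.3% |
| 8% | 7.6 | 5.5 | 14.3% |
| 12% | 5.2 | 3.7 | 20.3% |
| 15% | 4.2 | 3.0 | 24.4% |

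**Step 4: what the category records for the flat-weight child.** The change is 0%, which is below 5%, so the child is not counted at any g. This step needs no assumption about growth. A child who loses 4.9% is also not counted; at g = 5% and 12% that child is 1 − 0.951/(1+g)² = 13.7% and 24.2% below expected weight at 2 years.

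**Step 5: check against a growth reference.** Measured against expected weight, the normally growing child deviates by 0% and the flat-weight child by the last column. For a fully grown patient (g = 0) the two measures coincide, so the percent rule loses nothing in the 18 to under 21 group.

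**The case against.** The other side has several sound points.

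- **The category carries no label and no action.** SAP 9.1.3.4 only sorts data into categories. It calls none of them abnormal and attaches no test or decision. A reader might infer that the SAP declares normal growth an abnormality, or that it borrowed an adult rule. The text supports neither; it shows a fixed rule without age adjustment.
- **Two years is the cap, not the expectation.** In the paediatric Phase 1 study the median was 1 cycle, range 1-9 (Protocol Appendix 2). Median PFS on sunitinib in the adult Phase 3 trial was 22.9 weeks, about 5.3 months (Protocol Table 2). Against that, Protocol 1.1 describes a more indolent course in children, so longer exposure is plausible. At 1-2% gain per year, as in a nearly grown adolescent, the category is not reached at all. A reader might conclude that most children would be counted wrongly; that needs a growth rate and an exposure the documents do not give.
- **Real losses remain visible.** A fall of 5% or more still enters the category, and nothing prevents the two directions being shown apart.
- **There are other routes.** Abnormal examination findings after screening are reported as adverse events (Protocol Schedule of Activities, note 6). AEs are tabulated and listed by patient (SAP 9.1.3.1). Bone age and Tanner stage are collected (Protocol 7.3), and possibly treatment-related growth delays are reportable after follow-up (Protocol 6.3.2). It would be wrong to say that this row is the only place a weight problem could appear.

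These points limit the reach of the concern. They do not change what the planned display does with a growing child or with flat weight, and none of the other routes is a planned analysis of growth.

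**Conclusion.** The point holds as a minor improvement to a descriptive display. Two parts rest on the documents and arithmetic alone: flat weight is never counted, and a sustained gain of about 2.4-2.5% per year enters the category by the end of full treatment. The remaining figures (entry after about 12 to 5 months; a deficit of about 9-20% at 2 years) rest on an assumed constant gain of 5-12% per year. They apply only to children who are still growing and stay on treatment long enough.

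The PK endpoint and the efficacy analyses are unaffected. The documents do not show how many of the 6 children would be misread, and no such count should be claimed. The likely background is that the SAP follows a protocol version older than the growth assessments.

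**What to change.** For patients under 18, SAP 9.1.3.4 should:

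- summarise, and list by patient, the change from baseline in weight-for-age and height-for-age z-score;
- name one growth reference for all sites. The CDC charts are a candidate, but Protocol Appendix 3 cites them only for height percentiles ("The BP tables use height percentile data found on the CDC growth charts"), so their use for weight would be a new choice to state;
- fix any z-score cut-off before the analysis, or use none and rely on the listings, which is workable with 6 children.

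For all patients, show increases and decreases in separate columns. Keep the percent-change category for young adults, and keep weight loss of 5% or more as a category at any age.

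The cost is SAP wording and a small derivation from height, weight, age and sex, with no new procedure. The real downside is that one reference population would be applied to a multinational sample. Protocol 6.2 itself notes that local standards may differ, so the SAP should acknowledge this. Reading each child's change from his or her own baseline limits the effect.

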### **9.1.3.5. Electrocardiograms (ECGs)**

Triplicate, 12-lead ECGs are performed at Screening, Day 1 of Cycle 2, and at the end of treatment. At each time point, triplicate data will be averaged and all summary statistics and data presentations will use the triplicate averaged data.

Individual patient ECG data listings will be generated. Changes from baseline in corrected QT (QTc) interval will be calculated to describe and display the frequency of patients who experienced QTc interval prolongation, displayed by category according to CTCAE v4.0 grades. QT intervals will be corrected for heart rate using cube root (Fredericia's) conversion.

### **9.1.4. Analysis of Other Endpoints**

Descriptive statistics will be used to summarize study conduct and patient disposition, baseline characteristics, and treatment administration/compliance.

---

Protocol A6181196 Statistical Analysis Plan - Version 1.0 Final

---

**Study Conduct and Patient Disposition** - An accounting of the study patients will be tabulated. Patients not meeting the eligibility criteria and/or who deviate from the protocol will be identified. Patients not completing the study will be listed along with the reason for their premature discontinuation. Reasons for premature discontinuation will be summarized. The full analysis population will be used for the summarization of study conduct and patient disposition.

**Baseline Characteristics** - Demographic characteristics such as patient age, gender, height, weight, ethnicity, prior therapy, medical history, tumor history, Lansky/ECOG performance status and signs and symptoms will be tabulated. The full analysis population will be used for the analysis of baseline characteristics.

**Treatment Administration/Compliance** - Study drug administration will be described in terms of the total number of cycles administered, the median (range) of cycles administered, dose adjustments, dose interruptions, and reasons for the deviations from planned therapy. The per protocol population will be used for the summarization of treatment administration and compliance.

**Tumor Genetic Testing Data** – Results of tumor genetic testing will be presented descriptively without formal statistical testing.

**PET analysis** – Results of PET scans will be described but no formal statistical testing will be conducted.
